**Study RWE-003**

Title	Real-World Evidence (RWE) of Usage of Nerivio, a Remote Electrical Neurostimulation (REN) Device In Adolescents Patients With Migraine
Sponsor	Theranica Bio-Electronics Ltd. [name]
Investigational Device	
Nerivio is a Remote Electrical Neuromodulation (REN) wearable, battery-powered medical device for the acute and/or preventive treatment of migraine with or without aura in patients 12 years of age or older. Nerivio is controlled by a mobile application. Nerivio is intended for self-administration in a home healthcare environment.
 
The device is worn on the upper arm and transmits transcutaneous remote electrical nerve stimulation by applying weak electrical pulses that invoke conditioned pain modulation (CPM) to inhibit migraine pain. Nerivio is intended for self-administration at the onset of a migraine episode.

Objectives	To evaluate the safety, utilization and efficacy of Nerivio in adolescent patients (Age 12-18) who used the Nerivio device for treating their migraine
Patient Population	Nerivio users aged 12-18 years old who registered a Nerivio account and used the Nerivio device for the acute treatment of migraine.
Sample size	The sample size will includes all Nerivio users in the age of 12-18 in the Nerivio database who treated with Nerivio at least once between Jan 01, 2021 and May 31, 2022
Inclusion criteria	

• Age between 12-18 years

• REN user across the United States who created Nerivio account on January 1st, 2021 until May 31, 2022.

• Had at least two evaluable treatments with the Nerivio device (for consistent efficacy analysis).

Exclusion criteria	

• Treatments shorter than 20 minutes will not be included in the analysis

Study Design	
The analysis included patients at the age of 12-18 (at the day of opening a Nerivio account) with migraine across the USA who used Nerivio at least once between January 01, 2021, and May 31, 2022.
 
Treatment data will be collected through the Nerivio app (Nerivio®) which is required for treatment. Device output current is set by the user to be strong but not painful and is equivalent to treatment dosage (max device current 40 mA on 0-100 units user-facing scale). Additionally, patients can voluntarily log details about their symptoms at both treatment onset and 2-hours post-treatment status. Treatment efficacy will be measured by consistent reduction in headache pain intensity and functional disability at 2-hours post-treatment, based on data from patients who voluntarily will answer the pre and post treatment questionnaires. Safety will be assessed by the rate of device related adverse event reported by the patients.

Evaluable Treatment	
Evaluable treatment is a treatment that meets all the following criteria:
 

• Baseline and 2-hour post-treatment pain intensity and functional disability scores were recorded.

• The participant did not use any concomitant acute migraine medication during the treatment.

Efficacy endpoints	

1. Pain Relief: Reduction in pain intensity from moderate or severe (baseline score of 2 or 3) to mild or no pain (score of 1 or 0) at 2 hours post-treatment.

2. Pain Freedom: Reduction in pain intensity from mild, moderate, or severe (baseline score of 1, 2, or 3) to no pain (score of 0) at 2 hours post-treatment.

3. Functional Disability Relief: Reduction in functional disability by at least one point from baseline at 2 hours post-treatment.

4. Functional Disability Freedom: Reduction in functional disability from mild, moderate, or severe (baseline score of 1, 2, or 3) to no disability (score of 0) at 2 hours post-treatment.

Utilization endpoints	

5. Consistent Usage of Migraine Abortive (Rescue) Medications: The proportion of subjects with REN treatments without the use of pharmacological migraine abortive (rescue) medication (either over the counter or prescribed), or with a combination of rescue medication or without any treatment at all at 2 hours post-treatment in at least 50% of all their treatments.

6. Treatment intensity distribution: The mean intensity of the stimulation collected for all treatments that were performed within the study

Safety endpoints	Rate of serious adverse events, adverse events and device-related adverse events

Data collection	
Data will be collected prospectively through the Nerivio smartphone application. At the time of creating a Nerivio account on the App, patients (and their parents, in case of patients younger than 18) are required to sign a consent statement presented to them, where they agree that their deidentified data may be collected and used for reserve purposes.
 
Prospective data was collected for Nerivio users in the United States who treated their migraine attacks with the Nerivio device. Nerivio utilization, and Nerivio treatment reports at T=0h and T=2h were extracted from the Nerivio server in an unidentified manner. Data will be analyzed per user following additional analysis per the target population.
 
The following data will be extracted:
 

• Demographics: Age at registration, gender.

• Treatment Details: Treatment date, baseline pain intensity, pain intensity at 2 hours post-treatment, baseline functional disability, functional disability at 2 hours post-treatment.

• Treatment Frequency: Number of treatments per month over the 12-months period.

• Pain Intensity: 0 (no pain), 1 (mild), 2 (moderate), 3 (severe).

• Functional Disability: 0 (no disability), 1 (mild interference), 2 (moderate interference), 3 (severe interference).

• Additional migraine symptoms (Nausea/ vomiting, Photophobia, Phonophobia)

Statistical considerations	See at the end of the document
Responder Definition	For each efficacy endpoint, a participants will be considered a responder if they achieved the defined outcome in at least 50% of their evaluable treatments during that study period.

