### **Safety Endpoints Analysis**

The rate of device related adverse event (DRAE) will be calculated as the number of reported DRAE divided by the number of participants in the study.

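### Cohort entry rests on account date in the inclusion criteria but on treatment date in the sample size and study design rows, and the rules select different users

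*Combined protocol and SAP*

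**What the plan says.** The synopsis of the combined protocol and SAP states who enters the study in three dated places.

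- **Inclusion criteria row.** Entry depends on when the account was opened: "REN user across the United States who created Nerivio account on January 1st, 2021 until May 31, 2022".
- **Sample size row.** "The sample size will includes all Nerivio users in the age of 12-18 in the Nerivio database" with one condition, namely users "who treated with Nerivio at least once between Jan 01, 2021 and May 31, 2022". Account date is not mentioned.
- **Study Design row.** US patients with migraine "who used Nerivio at least once between January 01, 2021, and May 31, 2022". Account opening appears here only as the reference date for age: "patients at the age of 12-18 (at the day of opening a Nerivio account".

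The Patient Population row gives no dates: "Nerivio users aged 12-18 years old who registered a Nerivio account and used the Nerivio device for the acute treatment of migraine".

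Two planned analyses depend directly on who is in the cohort. Safety Endpoints Analysis defines the device-related adverse event rate as "the number of reported DRAE divided by the number of participants in the study". Efficacy Endpoints Analysis plans a generalized linear mixed model for the effect of treatment month on the efficacy rates.

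**The concern.** The dates agree in all three rows, but the qualifying event does not. Registration in the window gives a cohort of newly registered users. Treatment in the window adds anyone with an older account who was still using the device. Two analysts working from this plan could extract different datasets, and each could cite the text.

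The two groups may differ in more than size. A person who registered before 2021 and was still treating in 2021 or 2022 is a continuing user. If people who got little benefit, or did not tolerate the device, tended to stop, those who remain are selected on past response. Their early treatments may also predate the window, so the first month seen in the data need not be their first month of use. That bears on the treatment-month model, the only efficacy model the plan names. Leaving the rule open also allows the cohort to be settled after the data have been seen.

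**Working it through.** The plan gives no numerical sample size, power or count of users by registration date, so there is no figure to reproduce. The check is to apply each rule to every relevant type of user, taking US users aged 12-18 throughout.

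| User type | Inclusion criteria (account in window) | Sample size row (treated in window) | Study Design row (used in window) |
|---|---|---|---|
| 1. Account before 1 January 2021, at least one treatment in the window | Out | In | In |
| 2. Account in the window, at least one treatment in the window | In | In | In |
| 3. Account in the window, first treatment after 31 May 2022 | In on account date | Out | Out |
| 4. Account before 1 January 2021, no treatment in the window | Out | Out | Out |

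The rules agree on types 2 and 4 and disagree on types 1 and 3. The cohort under the inclusion criteria is types 2 and 3; under the other two rows it is types 1 and 2.

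Could other text settle the matter?

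1. The account-opening phrase in the Study Design row fixes when age is measured. It sets no earliest or latest date for the account.
2. The Patient Population row requires both an account and use, but dates neither.
3. The requirement of two evaluable treatments carries no dates, and its parenthesis ties it to the consistent-efficacy analysis. It does not separate type 1 from type 2.
4. No section ranks one row above another.

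What changes with the choice:

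- **Safety.** The denominator is the number of participants, so moving types 1 and 3 in or out changes it, and the events counted with it.
- **Treatment month.** The window runs for 12 + 5 = 17 months (January 2021 to May 2022), while the Data collection row refers to treatment frequency over 12 months. No origin for treatment month is defined. If month is counted from the start of the window, or treatments before it are dropped, type 1 users enter partway through their use.
- **Responder status.** A responder is judged on evaluable treatments in the study period. If that period is the window, a type 1 user is judged on later treatments only.

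The number of users of types 1 and 3 is not given, so the effect on sample size cannot be computed.

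**The case against.** The strongest defence is that only one of the three rows is an eligibility criterion, and that the other two are summaries. On that reading a user with an older account is simply out, and the workable cohort is type 2: registered and treated in the window. This is a sensible reading and the fix below adopts it. It does not dispose of the point, because the Sample size row claims all users who treated in the window. If account date also limits entry, that row is wrong as written, and nothing states precedence.

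A second objection is that the affected group may be small or empty. No section says that any adolescent held an account before 2021. That stands, and it limits what can be claimed about consequences.

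A reader might go further and infer that the plan inflates responder rates and understates adverse events. The documents do not support this.

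- **Responder rate.** The shift from adding earlier registrants is x × d, where x is their share of the cohort and d is their responder rate minus that of new users. Assuming x of 10-30% and d of 10-20 points gives 0.1 × 10 = 1 point to 0.3 × 20 = 6 points. Both inputs are assumptions, and a negative d would reverse the sign. The stated objective concerns adolescents who used the device, not those starting it, so including continuing users is a bias only if a new-user cohort is intended.
- **Adverse events.** The rate uses no person-time, and the Safety Data section sets no date limit on the reports drawn in. Users with longer exposure could contribute more events per participant, so a downward effect is not established.
- **Month effect.** Distortion depends on how month is counted and whether earlier treatments are dropped. Neither is stated. The missing origin is a gap for new users as well.

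**Conclusion.** The contradiction is real and stands in current text. Account creation governs entry in one row and treatment governs it in two; the rules disagree on two of the four user types, and they cannot all be followed. This conclusion rests on the wording alone.

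The consequences are less certain. The choice determines the analysed cohort, the adverse event denominator and the content of the treatment-month model. Earlier registrants would be continuing users who may be selected on past response. How many there are, and how far and in which direction they would move any result, cannot be derived from the documents. The point should be fixed because the remedy is cheap and every denominator depends on it. It does not show that the results are biased.

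**What to change.** Put the same entry rule in the Sample size, Inclusion criteria and Study Design rows: account created between 1 January 2021 and 31 May 2022, and at least one Nerivio treatment in that window. Both conditions are needed. The first matches the formal inclusion criterion; with it alone, users who registered in the window but had no treatment in it could still enter.

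In Efficacy Endpoints Analysis, define treatment month as counted from the user's own first treatment.

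If the sponsor prefers to keep users with earlier accounts, the plan should say so, identify them by account date, and report results with and without them. Counting month from first treatment would then require the dates of their treatments before 2021.

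The cost is wording in three rows and one sentence in the analysis section, with a possibly smaller sample if earlier accounts would otherwise have been counted. If the extraction has already been made, the sponsor should state which rule was applied. The change does not remove the selection that comes from voluntary reporting and the minimum of two evaluable treatments; those remain under any entry rule.

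### The two-evaluable-treatment rule stands as a study inclusion criterion and conflicts with the at-least-one-treatment population; the medication window and the entry-date rule are also stated in two incompatible ways

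*Combined protocol and SAP*

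**What the plan says.** All rows cited are in the synopsis table of the combined protocol and SAP unless stated otherwise.

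- **Who is in the study.** Inclusion criteria: "Had at least two evaluable treatments with the Nerivio device (for consistent efficacy analysis". Sample size: all users in the age range "who treated with Nerivio at least once between Jan 01, 2021 and May 31, 2022". Study Design: users "who used Nerivio at least once between January 01, 2021, and May 31, 2022".
- **Entry date.** Inclusion criteria: "REN user across the United States who created Nerivio account on January 1st, 2021 until May 31, 2022". The Sample size and Study Design rows date entry by a treatment in the window, not by account creation.
- **Which treatments count.** Evaluable Treatment requires baseline and 2-hour scores for pain and disability, and "The participant did not use any concomitant acute migraine medication during the treatment". Exclusion criteria: "Treatments shorter than 20 minutes will not be included in the analysis". In the SAP, under Utilization Endpoints Analysis, a *qualified* treatment lasts at least 20 minutes, has reports before and after, and has no rescue medication either beforehand or in the following 2 hours. The same section makes two qualified treatments a condition of the consistent-efficacy analysis.
- **Denominators.** The SAP's Safety Endpoints Analysis divides device-related adverse events (DRAE) by the count of study participants. The Safety endpoints row also lists SAE and AE rates, without a formula. Endpoint 5 classifies users by medication use "at 2 hours post-treatment in at least 50% of all their treatments". Endpoint 6 averages stimulation intensity over every treatment performed in the study.

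**The concern.** Safety and utilization are two of the three stated objectives. An inclusion criterion normally governs every analysis, so a rule written for efficacy reaches both of them from where it stands.

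Two groups would leave. Users who stopped after one treatment cannot have two evaluable ones. Users who do not log cannot have any, because efficacy is "based on data from patients who voluntarily will answer the pre and post treatment questionnaires". For safety, both groups should stay in the denominator. For endpoint 5 the problem is sharper: a treatment is evaluable only if it meets a medication-free condition, so requiring two of them selects users partly on what the endpoint measures.

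The medication window affects efficacy directly. Under the Evaluable Treatment row alone, a patient may take rescue medication after the session but before the 2-hour score, and the improvement can still count as a device response. The SAP rule excludes that treatment.

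The date rules also change membership. A user who registered before the window and treated within it is in under Sample size and Study Design, and out under Inclusion criteria.

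**Working it through.** The documents give no sample size, expected rate, treatments per user, logging rate or medication timing, so there is no planned figure to reproduce. The check sets the rules side by side and then illustrates their effect with assumed inputs.

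**Step 1: the rules compared.**

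| Item | One place | Another place | Compatible? |
|---|---|---|---|
| Treatments per user | Inclusion: two or more evaluable | Sample size, Study Design: one or more | Only if the first is an efficacy subset |
| Medication window | Evaluable Treatment: during the treatment | SAP: before it and for 2 hours after | No |
| Minimum duration | Exclusion criteria: 20 minutes | SAP: 20 minutes | Yes |
| Date rule | Inclusion: account created in window | Sample size, Study Design: treated in window | No |
| Short sessions | Exclusion: out of the analysis, scope not given | Endpoint 6: all treatments performed | Not stated |

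**Step 2: a case that needs only arithmetic.** Take the SAP's medication rule, with every treatment reported and at least 20 minutes long. A user with 2, 3 or 4 treatments, of which at least 2 are medication-free, is medication-free in at least 2/4 = 50%. Every such user who passes the rule therefore meets the 50% threshold. Without the rule, among users with 4 treatments and independent per-treatment probability p:

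P(K ≥ 2) = 1 − (1−p)^4 − 4p(1−p)^3

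- p = 0.3: 1 − 0.2401 − 0.4116 = 34.8%
- p = 0.5: 1 − 0.0625 − 0.2500 = 68.8%
- p = 0.7: 1 − 0.0081 − 0.0756 = 91.6%

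**Step 3: a wider illustration, all inputs assumed.** Treatments per user, N, are uniform on a range and all logged. The medication-free probability is Beta with the stated mean and concentration 2 (wide spread) or 10 (moderate spread). K is the number of medication-free treatments. E = K + Binomial(N − K, s) is the number that count, where s is the share of medication-using treatments in which the medication falls after the session; s = 0 reproduces the SAP's medication rule. The comparison is P(K ≥ N/2) for all users against P(K ≥ N/2 given E ≥ 2).

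| N, mean, spread | All users | s = 0 (SAP rule) | s = 0.25 | s = 0.5 | s = 1 |
|---|---|---|---|---|---|
| 1–4, 0.4, wide | 45.6% | 100% | 74.5% | 58.8% | 47.4% |
| 1–10, 0.4, wide | 42.3% | 70.8% | 52.2% | 45.8% | 42.6% |
| 10–30, 0.4, wide | 38.1% | 46.6% | 38.5% | 38.1% | 38.1% |
| 10–30, 0.4, moderate | 31.9% | 33.1% | 32.0% | 31.9% | 31.9% |
| 1–10, 0.8, wide | 86.2% | not shown | 90.1% | 88.3% | 86.9% |

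Under the Evaluable Treatment wording, the shift runs from zero to 74.5 − 45.6 = 28.9 points. Under the SAP rule it reaches 100 − 45.6 = 54.4 points in the shortest-use case.

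**Step 4: safety, with invented counts.** Suppose 500 users and 10 DRAE reports, one per user: 10/500 = 2.0%. The N = 1–10, mean 0.4, s = 0.25 case keeps 68.8% of users, or 344. If 2, 5 or 8 of the reports leave with the removed users, the rate is 8/344 = 2.3%, 5/344 = 1.5% or 2/344 = 0.6%. If none leave, it is 10/344 = 2.9%. The rate can go either way.

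**The case against.** The strongest reply is that the intended design can be read from the text. The criterion carries its own limit in the bracket, the SAP states the two-treatment rule as a condition of the consistent-efficacy analysis only, and two rows describe users treated at least once. Endpoint 5 has a category for treatments combined with rescue medication, which a medication-free filter would largely empty. All this favours a cohort treated at least once with an efficacy subset inside it. I accept that as the likelier intent. What stands is that the row is headed Inclusion criteria and nothing limits its effect on the other analyses.

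A reader might infer four stronger points, which the documents do not support:

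- *That safety and utilization have no denominators.* The SAP gives one for DRAE, and endpoints 5 and 6 state which treatments they cover. What is open is which users are study participants, which users endpoint 5 counts, and the SAE and AE formulas.
- *That evaluable and qualified treatments differ on duration.* The exclusion row and the Evaluable Treatment row together already match the SAP's 20 minutes. The medication window is the clear difference.
- *That endpoint 5 will be badly inflated.* This depends on study-wide use of the rule and on assumed inputs. At a mean of 0.8 with 1–10 treatments, the shift under the Evaluable Treatment wording is at most about 4 points.
- *That many treatments per user make the issue harmless.* With 10–30 treatments and wide spread, the SAP rule still gives 38.1% to 46.6%.

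**Conclusion.** The point holds as a conflict between stated rules, and should be fixed. Three collisions are plain from the text and need no assumption: two treatments against one, the two medication windows, and account date against treatment date. The scope of the 20-minute exclusion for endpoint 6 is a smaller gap of the same kind.

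The effect on results is conditional. If the inclusion list is applied study-wide, the medication-free share in endpoint 5 could move by anything from near zero to tens of points, depending on treatments per user, medication timing and the mean medication-free probability, none of which the plan reports. No direction is claimed for safety. Under the nested reading the endpoint 5 and safety effects largely disappear, but the medication-window and date conflicts remain. Confidence is high for the inconsistency and low for any particular size.

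**What to change.** 1. Move the two-treatment rule from Inclusion criteria to a named consistent-efficacy set.
2. Use all eligible users with at least one treatment as the denominator for the DRAE, AE and SAE rates, and as the users counted in endpoint 5. Keep that endpoint's basis of all treatments per user, and report how many treatments lack a medication answer.
3. Reconcile *evaluable* and *qualified* into one analysis definition, with one medication window covering the time up to the 2-hour assessment. Use it for endpoints 1–4, the responder denominator and the mixed model (GLMM). This concerns which treatments are analysed, not how patients are managed.
4. Reconcile the account-date and treatment-date rules.
5. State whether the 20-minute exclusion applies to endpoint 6.

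The cost is wording and a little more analysis, with no new data collection. The medication-free or efficacy figures may come out less favourable. If the nested design was already intended, items 1 and 2 mainly write it down.

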### **Utilization Endpoints Analysis**

Utilization outcome will be calculated from the treatment parameters (intensity levels) and the treatment reports (usage of rescue medications), and will be presented in appropriate distribution tables.

Qualifies treatment was defined as

1 - Attacks treated with Nerivio for at least 20 minutes

2 - Pre and post treatment data were reported by the participant for the specific treatment

3 – No rescue medications were taken before and during the 2 hours post treatment, according to the participant report

Consistent efficacy will be conducted in cases where at least two qualified treatments were performed. Patients who experienced the outcome (e.g., pain freedom) in at least 50% of their reported treatments, during which they did not report the use of rescue medications, were considered responders.

Headache pain and functional disability will be rated at baseline and at 2 h post-treatment on a 4-point scale: severe, moderate, mild, or none. Migraine associated symptoms (photophobia, phonophobia, and nausea/vomiting) will be marked as present or not.

Pain relief will be calculated as a decrease from severe or moderate levels at baseline to mild or none at 2 h posttreatment.

Functional disability relief will be calculated as any improvement in disability from baseline to 2 h posttreatment.

Pain/functional disability freedom will be calculated as a decrease from any pain/disability level at baseline to none at 2 h post-treatment.

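### Requiring both pain and disability scores before a treatment counts for any efficacy endpoint can discard attacks whose outcome on that endpoint is fully known; the size of the loss is unknown and may be zero

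*Combined protocol and SAP*

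**What the plan says.** In the synopsis, the Evaluable Treatment row sets a conjunctive rule: "Evaluable treatment is a treatment that meets all the following criteria". The first criterion is that "Baseline and 2-hour post-treatment pain intensity and functional disability scores were recorded", which means four scores per attack. The second concerns concomitant acute medication and is not at issue here.

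Two other synopsis rows rest on this set:

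- Inclusion criteria: "Had at least two evaluable treatments with the Nerivio device". A parenthesis ties this minimum to the consistent-efficacy analysis.
- Responder Definition, worded for each efficacy endpoint: "a participants will be considered a responder if they achieved the defined outcome in at least 50% of their evaluable treatments".

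The Study Design row says that "patients can voluntarily log details about their symptoms at both treatment onset and 2-hours post-treatment status".

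The statistical section, under Utilization Endpoints Analysis, has a parallel definition of a qualified treatment. Its reporting condition is "Pre and post treatment data were reported by the participant for the specific treatment", and it too sets a minimum of two such treatments for consistent efficacy. It does not say which scores are needed.

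**The concern.** Each endpoint in the Efficacy endpoints row is determined by two scores. Pain relief and pain freedom use pain at baseline and 2 hours. The two disability endpoints use disability at the same times. An attack with both pain scores and a blank disability item therefore has a known pain outcome, but the rule removes it from the pain endpoints. The reverse holds for the disability endpoints.

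Two things are at stake. Users with few reported attacks can fall below the two-treatment minimum. Users who stay can have their responder proportion recomputed on fewer attacks, for a reason unrelated to the endpoint. Efficacy already rests on users who choose to report, and the rule would narrow that group further, towards those who complete every item. The plan gives no reason for the joint requirement and has no rule for a missing item.

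**Working it through.** **Reading the rules together.** The plan states no sample size, blank rate or loss, so there is no figure to reproduce. The Evaluable Treatment row requires all four scores. The Responder Definition makes those treatments the denominator for every efficacy endpoint, and the Inclusion criteria require two of them. No section gives an endpoint-specific set. The qualified-treatment condition in the statistical section is vaguer: it could be read per endpoint, but it does not cancel the explicit rule in the synopsis.

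**Chance of falling below two evaluable treatments (illustration).**

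Inputs:
- the minimum of 2, from the Inclusion criteria;
- k, the number of a user's attacks with both pain scores and every other criterion met (assumed);
- m, the share of those attacks with a disability score missing (assumed, independent between attacks).

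The number of evaluable attacks is Binomial(k, 1 − m), so

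P(fewer than 2) = m^k + k(1 − m)m^(k−1).

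Worked cases:
- k = 2, m = 0.10: 0.01 + 2 × 0.9 × 0.1 = 0.190
- k = 3, m = 0.20: 0.008 + 3 × 0.8 × 0.04 = 0.104
- k = 4, m = 0.30: 0.0081 + 4 × 0.7 × 0.027 = 0.0837

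| k | m = 5% | m = 10% | m = 20% | m = 30% |
|---|---|---|---|---|
| 2 | 9.8% | 19.0% | 36.0% | 51.0% |
| 3 | 0.7% | 2.8% | 10.4% | 21.6% |
| 4 | 0.05% | 0.4% | 2.7% | 8.4% |

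At k = 10 the chance is about 0.01% or less for every m shown.

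**If blanks cluster by user.** At the other extreme, a share m of users always skips the disability item and the rest never do. The loss is then m at every k: 10%, 20% or 30%. That is lower than the independent figures at k = 2, higher from k = 3 on, and it does not shrink with more attacks.

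**Responder status without exclusion.** Take a user with pain relief in 2 of 4 pain-complete attacks: 2/4 = 50%, a responder. If one relieved attack lacks a disability score, the proportion becomes 1/3 and the user is a non-responder. If one unrelieved attack lacks it, the proportion is 2/3 and the user remains a responder.

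**Under endpoint-specific evaluability.** No pain-complete attack is lost to a blank disability item, so the loss from this cause is 0 at any m.

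**The case against.** The strongest objection is that no harm is shown. Nothing in the documents says a pain score can be entered without a disability score. The Study Design row also describes answering at the level of whole questionnaires. If the items are always completed together, the rule removes nothing. This stands: the effect is conditional and may be nil.

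A reader might infer that users are dropped from the study. The documents do not support that. The two-treatment minimum is tied to consistent efficacy, and the sample is described as users who treated at least once. The device-related adverse event rate divides by participants in the study, and the utilization endpoints refer to all treatments. Nor does one blank remove a user by itself; the user leaves only if fewer than two evaluable treatments remain.

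A reader might also take the 19% to 51% figures as the expected loss. They apply only to users with exactly two pain-complete attacks, a share the documents do not give, and they assume independent blanks.

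It can be said that the statistical section's looser definition would govern. It does not name the scores, so it leaves unsettled which rule would be run. That is a reason to align the two definitions.

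Finally, a common set lets pain and disability results be compared on the same users and attacks. This is a real advantage, although the plan does not claim it. A sensitivity analysis on the four-score set preserves it.

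**Conclusion.** The point holds as a defect in the stated rule, with an effect of unknown size. Read as written, the synopsis excludes an attack from an endpoint because a score that the endpoint does not use is missing, and the statistical section does not clearly correct this. The consequence is limited to the efficacy analyses. With independent blanks, the loss of users falls mainly on those with two or three reported attacks; with blanks clustered by user it would not fade with more attacks. All percentages rest on assumed blank rates. The documents support neither a claim that data have been lost nor a direction of bias. The change is still worth making: it recovers valid outcomes if blanks occur and alters nothing if they cannot.

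**What to change.** Define evaluability by endpoint, in identical words in the synopsis (Evaluable Treatment) and the statistical section (qualified treatment):

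- Pain relief: baseline and 2-hour pain recorded, with baseline pain 2 or 3.
- Pain freedom: baseline and 2-hour pain recorded, with baseline pain at least 1.
- Disability relief and disability freedom: baseline and 2-hour disability recorded, with baseline disability at least 1.

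The baseline conditions follow from the endpoint definitions. Without them, for example, an attack with mild baseline pain stays in the pain-relief denominator although it cannot meet the endpoint.

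The other criteria for an evaluable treatment are not touched by this change. Apply the two-treatment minimum, in both places where it is stated, within each endpoint. Report users and treatments per endpoint and the number lost to each missing item; state whether the app allows single items to be skipped. Keep the four-score set as a sensitivity analysis.

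The cost is small. All four scores are already on the extraction list, so no new data are needed, but the wording changes in more than one place. Denominators will differ between endpoints and must be shown with each result.
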